5.2.4 Arm B: Midostaurin Administration

Midostaurin 50 mg (two 25 mg capsules) twice a day by mouth on days 8-21 (if chemotherapy were to have begun in the evening, then it is possible that the scheduled midostaurin administration on day 8 may occur on calendar day 9). Patients should take their doses at approximately the same time each day, and approximately 12 hours should elapse between the morning and evening doses. Each daily dose should be given with food and a glass of water (~240 mL). Patients should be instructed to swallow capsules whole and not open, break or chew capsules. If vomiting occurs, no re-dosing is allowed prior to the next scheduled dose.

When patients are hospitalized for treatment (i.e. induction, aplasia or events), midostaurin will be administered per site procedures for inpatient study management. Instructions to patients and study staff regarding the above recommendations for administration should be included in orders or related patient record documentation, including drug handling and disposal.

Compliance in taking assigned dose of midostaurin (commercial stock) when the patient is not hospitalized, will be assessed by a medication diary. Patients should be instructed to bring medication diaries to the site at each visit, for staff review. Patients may be counseled by the study staff regarding adherence concerns.

Dose interruptions are permitted (Section 6). Missed doses are not made up. Assigned treatment should continue through induction and consolidation cycles until unacceptable toxicity occurs, or the patient meets a treatment discontinuation criterion as provided in Section 6 and/or Section 7.3.

## 6. Dose Modifications

### 6.1 Dose Interruptions & Reductions

All toxicities should be graded according to the National Cancer Institute (NCI) Common Terminology Criteria for Adverse Events Version 5.0 (CTCAE V5.0). A copy of the CTCAE V5.0 can be downloaded from the CTEP website (<http://www.ctep.cancer.gov>).

Delays due to holidays, weekends, or other unforeseen circumstances will be permitted.

#### 6.1.1 Arm A and Arm B: Daunorubicin

Initial and subsequent daunorubicin doses should be reduced as follows for hepatotoxicity (Table 6-1):

Table 6-1: Daunorubicin Hepatotoxicity Dose Reduction	
Direct Bilirubin	Dose Reduction
<2	None
2-3	25%
>3	50%

For patients with evidence of hepatic dysfunction, reassess regularly per institutional standards during induction treatment.

#### 6.1.2 Arm A: Gilteritinib

The dose levels include the following (Table 6-2):

Table 6-2 Gilteritinib Dose Levels	
Dose Level (DL)	Gilteritinib Dose
DL 1 (starting dose)	120 mg
DL -1	80 mg
DL -2	40 mg

The gilteritinib dose may be initially reduced by 1 dose level for a described instance meeting criteria for dose reduction. The study drug dose can be further reduced by a second dose level. Note that dose reductions should occur in a step-wise manner. Only 2 dose level reductions are permitted. Dose re-escalation is not allowed following dose reduction unless there is a specific reason not related to gilteritinib for temporarily holding or reducing gilteritinib.

Gilteritinib will be interrupted per Table 6-3. When the grade of the adverse event (AE) decreases to  $\leq 1$ , study drug may be resumed at the next lower dose level, unless the investigator deems the AE was, in retrospect, unlikely to be or not related to the study drug, at which point the original dose may be resumed.

Additionally, if the investigator deems it necessary to ensure subject safety, dosing may be interrupted or reduced for reasons other than those provided in Table 6-3. In the unusual circumstance that dosing is interrupted or reduced for reasons not specified in the table, the investigator should promptly inform PrECOG.

Missed doses of gilteritinib will not be made up.

Table 6-3 Guidelines for Gilteritinib Dose Interruption or Reduction Event	
Event	Action
First occurrence: Grade $\geq$ 3 nonhematological AE possibly, probably or definitely related to the study drug (excluding pancreatitis, see below)	Dosing will be interrupted. If the AE resolves to $\leq$ grade 1 within 14 days, the patient may resume dosing at the reduced dose during this or subsequent cycles. If the AE does not resolve to $\leq$ grade 1 within 14 days, the subject will be discontinued from treatment and an end of treatment visit will be performed.
Second occurrence: Recurrence of the same nonhematological AE or appearance of other new nonhematological AE Grade $\geq$ 3 probably, possibly or definitely due to the study drug (excluding pancreatitis, see below)	Dosing will be interrupted. If the AE resolves to $\leq$ grade 1 within 14 days, the patient may resume dosing at the reduced dose during this or subsequent cycles. If the AE does not resolve to $\leq$ grade 1 within 14 days, the subject will be discontinued from treatment and an end of treatment visit will be performed.
Third occurrence: Recurrence of a prior nonhematological AE or appearance of other new nonhematological AE Grade $\geq$ 3 probably, possibly or definitely due to the study drug (excluding pancreatitis, see below)	The study drug will be discontinued.
At any point, in retrospect, if the investigator determines prior non-hematological Grade $\geq$ 3 AE which was initially attributed as possibly, probably or definitely related to study drug is now deemed unrelated	The study drug will be re-escalated to dose that the participant was on at the time of the AE.
Pancreatitis	Dosing will be interrupted until pancreatitis is resolved, then resume gilteritinib at 80 mg during this or subsequent cycles.
QTcF >500 ms	If the QTcF is >500 ms at any time point, the ECG will be repeated (within 2 hours or as soon as possible). Confirm that potassium and magnesium abnormalities are corrected. A cardiology consult will be obtained as medically indicated. If the repeat ECG confirms a QTcF >500 ms, dosing of study treatment will be interrupted. If QTcF resolves to $\leq$ 480 ms within 14 days from study drug interruption, subsequent dosing will be reduced to 80 mg (or if currently at 80 mg, reduction to 40 mg).
QTc interval increased by >30 msec over screening on ECG on Day 15 of Cycle 1	Confirm with ECG on Day 16. If confirmed, consider dose reduction to 80 mg. If currently at 80 mg, dose reduction to 40 mg.
Posterior Reversible Encephalopathy Syndrome (PRES)	Contact PrECOG, discontinue gilteritinib.

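### The re-attribution row of Table 6-3 sends a patient back to 120 mg of gilteritinib even when a later, still drug-related reduction stands; the target is at least one dose level too high

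*Protocol*

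**What the plan says.** Protocol Section 6.1.2 and its Table 6-2 set three gilteritinib dose levels: 120 mg (start), 80 mg and 40 mg. Reductions are step-wise and at most two are allowed, so two can stand at once for different reasons.

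The running text gives a general rule on going back up: "Dose re-escalation is not allowed following dose reduction unless there is a specific reason not related to gilteritinib for temporarily holding or reducing gilteritinib". For an AE that has resolved, it permits a return where the investigator, looking back, judges the event "unlikely to be or not related to the study drug, at which point the original dose may be resumed". It also lets the investigator act on safety grounds outside the table: "dosing may be interrupted or reduced for reasons other than those provided in Table 6-3".

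Table 6-3 has its own row for a change of attribution. It applies at any time, and its action is: "The study drug will be re-escalated to dose that the participant was on at the time of the AE". Other rows set lower doses for other reasons:

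- Second related Grade 3 or higher AE: after resolution, "the patient may resume dosing at the reduced dose during this or subsequent cycles".
- Confirmed QTcF above 500 ms that resolves to 480 ms or less within 14 days: down to 80 mg, or to 40 mg if already at 80 mg.
- QTc rise of more than 30 msec on Day 15 of Cycle 1, confirmed on Day 16: a reduction is to be considered. "If currently at 80 mg, dose reduction to 40 mg".
- Pancreatitis: wait for resolution, "then resume gilteritinib at 80 mg during this or subsequent cycles".

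**The concern.** The re-attribution row fixes its target from one fact only: the dose at the time of the event now judged unrelated. It does not ask what has happened since. If a second reduction was made for a different reason that is still attributed to gilteritinib, the row removes that reduction as well.

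At stake is the dose given to a patient who has already had a drug-related event at 80 mg. Section 1.3.4.1 reports 120 mg as the maximum tolerated dose with 7+3, so there is little margin above it.

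The row and the running text also differ in two smaller ways. The row is mandatory where the text is permissive. The row requires the event to be unrelated, while the text also accepts unlikely; Section 8.1 (Attribution) lists these as separate categories and counts both as not drug-related.

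**Working it through.** No figure in the plan can be reproduced here. The check is to trace dose paths through Section 6.1.2 and Tables 6-2 and 6-3.

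**Inputs.** Levels 120, 80 and 40 mg (Table 6-2). AE 1 occurs at 120 mg and is first judged related, so the dose falls to 80 mg. A later event follows and is still judged related. AE 1 is then deemed unrelated. An investigator safety reduction is taken as one level, in line with the step-wise rule.

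| Later event at 80 mg | Dose before re-attribution | Row gives | If only the AE 1 step is reversed | If the later step fixes the dose |
|---|---|---|---|---|
| Second related Grade 3 or higher AE | 40 | 120 | 80 | 40 |
| Confirmed QTcF above 500 ms | 40 | 120 | 80 | 40 |
| QTc rise above 30 msec (if the reduction is made) | 40 | 120 | 80 | 40 |
| Investigator reduction, related reason | 40 | 120 | 80 | 40 |
| Pancreatitis | 80 | 120 | 80 (pancreatitis row) | 80 |
| None | 80 | 120 | 120 | not applicable |

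**First four lines.** The general rule in Section 6.1.2 allows re-escalation only where the reason for the reduction is not related to gilteritinib. AE 1 now meets that condition; the later event does not. One step may be undone and one may not. Counting one surviving reduction from 120 mg gives 80 mg. Holding the dose that the later step set gives 40 mg. The text does not choose between them, but 120 mg fits neither. The excess is one level (120/80 = 1.5) or two levels (120/40 = 3).

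**Pancreatitis.** The only reduction was for AE 1, so the general rule is not breached. The conflict is between two rows of the same table, 120 against 80 mg.

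**Where there is no conflict.** With AE 1 alone, 120 mg is right. If AE 1 stands and only a second AE, which occurred at 80 mg, is re-attributed, the row gives 80 mg, which is right. If a QTcF reduction to 80 mg came before the re-attributed AE, the row also gives 80 mg, which is right. The 120 mg result therefore needs the re-attributed AE to have occurred at 120 mg and the standing limit to have come after it.

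**How rare.** Section 1.3.1 reports a maximum QTcF above 500 msec in 4.4% of relapsed or refractory patients. Assume the same rate in Arm A, with 85 patients (170/2) to 90 (179/2, rounded up):

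- 0.044 × 85 = 3.7 and 0.044 × 90 = 4.0 patients.
- At half the rate, 0.022 × 85 = 1.9; at twice the rate, 0.088 × 90 = 7.9.

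These are ceilings for the QTcF route. It also needs confirmation on repeat ECG, recovery to 480 ms or less within 14 days, an earlier reduction for AE 1, and the re-attribution of AE 1. The route through the 30 msec rise is narrower: AE 1 must start, resolve and be followed by a restart between Day 8 and Day 15, at most 7 days. The documents give no frequency for the other routes.

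**The case against.** The strongest reply is that Section 6.1.2 already contains the answer. Its general rule blocks re-escalation while a related reason stands, and its re-attribution sentence concerns the single event being re-judged. A careful investigator would read the row as reversing only its own step. The table is headed as guidelines, the re-attribution is the investigator's own decision, and the investigator may reduce for safety at any time.

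This softens the problem without removing it. The row does not say that it is limited to its own step, and nothing ranks the text above the table. The discretion offered is to reduce again after a directed increase.

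The reply is right on three further points:

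- The evidence of added harm is mixed. Section 1.3.1 reports dose-proportional exposure and a QTcF rise with concentration, but regards clinically relevant prolongation as not anticipated. Section 1.3.3 found no clear dose pattern for Grade 3 or higher or drug-related events.
- The 4.4% comes from a study that dosed 20 to 450 mg, so it is a loose guide to Arm A.
- Section 12.3.1 states that the interim analysis planned at 90 patients is complete. An amendment cannot help patients who have finished treatment, and the documents do not say how many remain on it.

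**Conclusion.** The defect is real and small. The row is a directed action that, in a specific order of events, gives a dose the surrounding text does not allow. In the two-reduction case 120 mg is at least one level too high. In the pancreatitis case two rows give different doses.

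Two stronger readings are tempting and should not be drawn. A reader might infer that 40 mg is the protocol's correct dose, and hence that the row triples it. The documents do not establish that: reversing only the AE 1 step gives 80 mg, and the text is silent between the two. A reader might also infer that the row overrides the pancreatitis row. No precedence is stated, and the 80 mg instruction remains in the table.

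The conclusion rests on reading the row literally, with AE 1 at 120 mg and a later cause still judged related. The sequence is rare, 120 mg is the Arm A starting dose and is never exceeded, and no endpoint, population or power figure changes. It is a low-priority safety-wording correction. Confidence is high that the exception is missing; which of 80 and 40 mg should apply is left open.

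**What to change.** Reword the row along these lines:

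> If a prior Grade ≥3 non-hematological AE is later deemed unlikely or not related to gilteritinib, only the reduction made for that AE may be reversed. Any other reduction or dose limit under Section 6.1.2 or Table 6-3 whose cause is still considered related to gilteritinib remains in force.

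Use the same permissive verb and the same attribution threshold in the Section 6.1.2 paragraph, so that text and table agree.

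The sponsor's medical monitor should also state whether the two-reduction case ends at 80 or 40 mg. Either is acceptable; 120 mg is not. This is a clinical choice, so the wording above does not make it.

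The cost is one table row and one paragraph at the next amendment, with no effect on data, endpoints or sample size. AE 1 alone can still return to 120 mg, and re-attribution of a second AE alone can still return to 80 mg. The downside is that a few patients stay on a lower dose than the row now gives. If 40 mg is chosen, that is below the 80 mg level from which Section 1.3.1 reports marked and sustained FLT3 inhibition.

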### 6.1.3 Arm B: Midostaurin

Interrupt midostaurin for Grade 3/4 non-hematologic toxicity thought to be possibly related to midostaurin and restart at same dose when toxicity resolves to  $\leq$  Grade 1. If the toxicity resolves prior to day 21, then restart at same dose to complete current cycle. Missed doses will not be made up.

For QTcF >500, confirmed on repeat study, check potassium and magnesium and correct any abnormalities. If at that time QTcF is >480, restart at 50 mg daily, until QTcF is  $\leq$  480. Once QTcF  $\leq$  480 restart at 50 mg BID.

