- 7 BUN/creatinine, uric acid, sodium, potassium, chloride, glucose, calcium, magnesium, and phosphorus. Additionally, required within 24 hours prior to each cycle of chemotherapy.
- 8 **Induction:** Twice weekly.  
**Consolidation:** Weekly or per institutional guidelines.
- 9 AST, ALT, and total bilirubin. If total bilirubin  $\geq 2$ , obtain direct bilirubin (if direct bilirubin  $\geq 2$ , refer to Section 6.1 for Dose Modifications/Interruptions). Additionally, required within 24 hours prior to each cycle of chemotherapy.
- 10 Thyroid Function test results not required for randomization.
- 11 Required for sexually active females of child-bearing potential.
- 12 LVEF must be obtained before initiating second induction cycle (if applicable) and must use same method as initial assessment.
- 13 Perform 12-lead ECG in triplicate (3 separate ECGs recorded at least 5 minutes apart) following a 10 minute resting period. Patient may not have QTcF interval >500 msec or Long QT Syndrome.  

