**Calculation of QTc interval using the Fridericia formula:**  
[https://qxmd.com/calculate/calculator\\_48/ecg-corrected-qt](https://qxmd.com/calculate/calculator_48/ecg-corrected-qt)
- 14 Perform 12-lead ECG in triplicate (3 separate ECGs recorded at least 5 minutes apart) following a 10 minute resting period prior to gilteritinib or midostaurin administration (ECG within 1 hour of dosing preferred). The mean QTcF of the triplicate ECG tracings will be used for final treatment decisions and AE reporting. If the mean of the triplicate QTcF is >500 msec, then triplicate ECGs will be repeated (within 2 hours). If the repeat ECGs confirm a mean QTcF >500 msec, refer to Section 6.1.2 and Section 6.1.3 for further guidance on treatment decision. In addition, on Cycle 1, Day 15 if QTcF is increased >30 msec over screening, repeat ECG on Day 16 and refer to Section 6.1.2 for further guidance on treatment decision.
- Induction (First Induction)**  
Day 8, Day 15 and Day 21
- Second Induction and Consolidation**  
Day 8 of each cycle
- See footnote 13 for Calculation of QTc interval using the Fridericia formula.**
- 15 Perform 12-lead ECG in triplicate (3 separate ECGs recorded at least 5 minutes apart) following a 10 minute resting period.  

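### The midostaurin QTcF rule states no hold at a confirmed value above 500 msec and puts no ceiling on restart, so read literally it directs dosing while QTcF is still above 500

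*Protocol*

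**What the plan says.** Protocol Section 6.1.3 has two short paragraphs on midostaurin.

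- **General toxicity.** "Interrupt midostaurin for Grade 3/4 non-hematologic toxicity thought to be possibly related to midostaurin and restart at same dose when toxicity resolves" to Grade 1 or lower.
- **QTcF.** "For QTcF >500, confirmed on repeat study, check potassium and magnesium and correct any abnormalities". The next sentence reads "If at that time QTcF is >480, restart at 50 mg daily", to continue until QTcF is 480 or lower. Once it is, the instruction is to "restart at 50 mg BID".

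Three other places bear on the same event:

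- Section 10, footnote 13, sets the entry limit: "Patient may not have QTcF interval >500 msec or Long QT Syndrome".
- Section 10, footnote 14, covers ECGs before either study drug: "If the repeat ECGs confirm a mean QTcF >500 msec, refer to Section 6.1.2 and Section 6.1.3 for further guidance on treatment decision". SAP Appendix I repeats this referral.
- Section 5.2.4, on midostaurin administration, says only "Dose interruptions are permitted (Section 6"), which again sends the site back to Section 6.

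**The concern.** The QTcF paragraph is the instruction a site is sent to when an Arm B patient has a confirmed QTcF above 500. Two things are missing from it. The first is an order to stop the drug: a hold can be inferred from the word *restart* but is never stated. The second is a ceiling on the restart condition. Any value above 480 qualifies for 50 mg daily, including the values above 500 that triggered the rule.

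The paragraph also does not say how it relates to the general toxicity paragraph just before it. That paragraph restarts at the same dose, requires recovery to Grade 1 or lower, and has no 50 mg daily step.

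At stake is patient safety and consistency between sites. A site that follows the words would dose a patient whose QTcF remains above 500 after electrolyte correction; another site would hold.

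The trigger is plausible in this population. Section 6.2.3 and Appendix V allow strong CYP3A inhibitors when used as standard anti-infectives. Section 11.2.5 says potent inhibitors could raise midostaurin concentrations and toxicity. Appendix V also lists azole antifungals among the drugs that may prolong QT.

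**Working it through.** The plan gives no figure to reproduce here. The check is to read each arm's rule as a decision table over the QTcF value that follows a confirmed reading above 500.

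**Inputs**

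- Arm B: Protocol Section 6.1.3, QTcF paragraph.
- Arm A: Protocol Section 6.1.2, Table 6-3, QTcF row. A confirmed value above 500 interrupts dosing. If QTcF falls to 480 or lower within 14 days, dosing resumes one level down (80 mg, or 40 mg if the patient was already on 80 mg).

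**Rules side by side**

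| QTcF after the confirmed event (for Arm B, after electrolyte correction) | Arm B, midostaurin, as written | Arm A, gilteritinib, as written |
|---|---|---|
| 480 or lower | 50 mg BID | Resume at reduced dose, if within 14 days |
| Above 480, up to 500 | 50 mg daily | Remains interrupted |
| Above 500 | 50 mg daily | Interrupted |

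The last Arm B cell follows because every value above 500 is also above 480. No Arm B branch withholds the drug.

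**Dose implied in that branch**

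- Assigned dose: 50 mg × 2 = 100 mg/day.
- QTcF step: 50 mg × 1 = 50 mg/day.
- Ratio: 50/100 = 50% of the assigned dose, for as long as QTcF stays above 480.

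**Search for a hold elsewhere**

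- Section 10, footnote 14, and its copy in SAP Appendix I refer back to Sections 6.1.2 and 6.1.3 and add no hold of their own.
- Sections 5.2.4 and 11.2.4 refer back to Section 6.
- Section 6.1.2 lets the investigator interrupt for safety reasons outside its table, but that text is about gilteritinib. Section 6.1.3 has no matching sentence.
- The general paragraph of Section 6.1.3 would order an interruption if the event were graded 3 or 4 and judged possibly related to midostaurin. Section 6.1 grades by CTCAE version 5.0, but the documents do not reproduce the QTc grade cut-offs, so whether it applies cannot be settled from them. If it does apply, its restart terms differ from those of the QTcF paragraph.

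**The case against.** The strongest reply is that a hold is presupposed. The QTcF paragraph speaks of restarting twice, and a drug that was never stopped cannot be restarted. Read together, the general paragraph would supply the interruption and the QTcF paragraph the specific restart terms, with the specific rule naturally governing. Footnote 14 also sends sites to Section 6.1.2, where an explicit hold is written. Other safeguards exist: triplicate ECGs with a repeat within 2 hours, and Sections 7.1 and 7.3, which allow treatment to stop for unacceptable toxicity, for harm to the patient's health or by investigator decision. The entry limit is an eligibility criterion, not an on-treatment threshold. A stepped lower dose could be a deliberate clinical choice.

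Much of this is fair. The hold is probably intended, many clinicians would hold anyway, and the entry limit is only supporting context. The precedence point is secondary, since most readers would let the specific rule govern.

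None of it supplies a ceiling. If a hold is granted, the text still ends it once electrolytes have been corrected, at any value above 480. The Section 6.1.2 table is headed for gilteritinib and does not formally bind Arm B. General discretion to stop does not correct a specific instruction that points the other way. A deliberate stepped dose could explain 50 mg daily between 480 and 500, but hardly an unstated hold together with a restart above the trigger level.

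**Conclusion.** The concern holds. Taken literally, Section 6.1.3 directs 50 mg/day of midostaurin, half the assigned dose, to a patient whose QTcF is still above 500 after electrolyte correction, and no branch of the QTcF rule withholds the drug.

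The conclusion concerns the wording. It does not assume that sites have dosed in this way. The rule applies to any Arm B patient with a confirmed QTcF above 500. The documents give no midostaurin frequency, so no patient count is offered. No efficacy analysis, power or error rate changes.

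Two things remain unknown from the documents: whether the Grade 3/4 paragraph would reach such an event under CTCAE, and whether any Arm B patient is still on drug. Section 12.3.1 says only that the futility analysis is complete and the study continues. The correction should be made: it concerns a safety instruction and costs very little.

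**What to change.** Amend the QTcF paragraph of Section 6.1.3 to state that:

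1. midostaurin is held when a QTcF above 500 msec is confirmed on repeat ECG;
2. it is not restarted while QTcF remains above 500, even after potassium and magnesium have been corrected;
3. this rule takes precedence over the general Grade 3/4 paragraph for QTcF events.

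The clinical team should confirm the restart threshold, and whether the 50 mg daily step is meant only for values above 480 and up to 500. If it is, the range should be written with both limits.

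The cost is one or two sentences at the next amendment and a notice to sites. No new data or procedures are needed, and the statistical analysis does not change.
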